# NURSE QUESTIONNAIRE – PROFESSIONAL OPINIONS ON APPLICATION

	S1F = UrgoK2		
	S1R = UrgoK2 Lite		
Bandage used: Right Leg			
	S2F = Coban2		
S1F/S1R, S2F/S2R or S3F/ S3R (circle what applies)	S2R = Coban2 Lite		
	S3F = AndoFlex TLC Calamine		
	S3R = AndoFlex TLC Lite Zinc		
On a scale of 1-6 (1 = worst, 6 = best) please rate the following as your overall			

On a scale of 1-6 (1 = worst, 6 = best) please rate the following as your overall clinical experience of using this compression system compared to previously used compression system (please circle):

How easy is it to apply? (i.e. speed, technique required such as simple spirals and visual indicators for correct tension, cutting, tapes)	1	2	3	4	5	6	
How easy is it to remove? (i.e. Wear time – appearance of the bandage post wear – slippage, unwind, worn out areas)	1	2	3	4	5	6	
How 'neat' does it look once it has been applied?	1	2	3	4	5	6	
Is it easy to learn how to apply it?	1	2	3	4	5	6	
Is it easy to teach others to apply?	1	2	3	4	5	6	
Do you like using this bandage			Yes	No N/a	a		

	S1F = UrgoK2
	S1R = UrgoK2 Lite
Bandage used: Left Leg	
	S2F = Coban2
S1F/S1R, S2F/S2R or S3F/ S3R (circle what applies)	S2R = Coban2 Lite
	S3F = AndoFlex TLC Calamine
	S3R = AndoFlex TLC Lite Zinc

On a scale of 1-6 (1 = worst, 6 = best) please rate the following as your overall clinical experience of using this compression system compared to previously used compression system (please circle):

compression system (preuse en cie).							
How easy is it to apply? (i.e. speed, technique required such as simple spirals and visual indicators for correct tension, cutting, tapes)	1	2	3	4	5	6	
How easy is it to remove? (i.e. Wear time – appearance of the bandage post wear – slippage, unwind, worn out areas)	1	2	3	4	5	6	
How 'neat' does it look once it has been applied?	1	2	3	4	5	6	
Is it easy to learn how to apply it?	1	2	3	4	5	6	
Is it easy to teach others to apply?	1	2	3	4	5	6	
Do you like using this bandage			Yes	No N/a	a		

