# **Study Protocol**

# **Project summary**

This study aims to provide explanations of when, for whom and in what circumstances are two different types of compression bandages (paste or dry) selected in the treatment of lower limb ulceration.

Compression bandages are used in the treatment of leg ulceration. A leg ulcer develops when blood vessels are not working as they should; they are painful, distressing and have a considerable impact on quality of life. They require frequent dressing changes, but with correct treatment can heal within three months. Evidence that compression is the gold standard to heal leg ulceration exists, but comparative data between different brands of compression bandages does not. Selection of a compression system is often based on nurses' preference, based on their acquired knowledge and skills of product application. This study aims to understand when, for whom and in what circumstances two very different product types should be selected to treat individual patient's lower limbs.

Patients have been the primary inspiration for this project. They often report that they are unable to tolerate compression bandages and when questioned in more detail, it appears that different systems have not been considered.

This study will use a research technique called 'realist evaluation', which acknowledges that leg ulcer care is complex, and is undertaken in a complex health care system. The process commences with listing what we think is happening (initial theories) and refine this through the analysis until the most plausible explanation is found.

The study is divided into two concurrent parts:

Patients who require bilateral compression bandages (registered with a Newcastle upon Tyne GP) will be selected from the caseload of District Nurses and Ambulatory Clinics.

- Opinions on the ease of application will be sought from Community Nurses and District Nurses who are applying the compression bandages to the recruited patients
- (ii) Opinions on comfort will be sought from the recruited patients.

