#### Research question and study aim

This research asks: 'When, for whom and in what circumstances are two different types of compression bandages selected in the treatment of lower limb ulceration?'

This study aims to provide explanations of when, for whom and in what circumstances are two different types of compression bandages selected in the treatment of lower limb ulceration. The premise is that all systems under review in this study work equally well, but it is unclear which system works best in the right patient, at the right time and in the hand of the right clinician.

The secondary objectives are to add to the body of knowledge that pertains to leg ulceration care and guide staff to select the right compression bandage for each patient.

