# **Recruiting and Screening**

Patients will be existing patients on the Newcastle upon Tyne Hospitals NHS Foundation Trust District Nursing's workload. Potential patients participants will be identified using Systm1, the electronic documentation system used by District Nurses in Newcastle. A list of potential participants will be drawn by the administrative team within District Nurses.

During the course of standard care, District Nurses will ask permission for the Research Nurse to contact them via telephone, letter or email. With agreeing, the District Nurse will enter the following text in the patient electronic documentation: "Mr/Mrs/Ms [Patient name] has agreed for the Research Nurse to contact him/her regarding the ROSE study". Upon contact, the Research Nurse will give potential patient participants the PIS and seek informed consent.

Thus Nurse participants will be involved in the recruitment process, and it is hoped that this will enhance their willingness to be recruited to the study alongside their patients.

Nurse Participants will be contacted by the Research Nurse who is a NuTH employee, through the existing nursing management structure.

In accordance with Good Clinical Practice, participation in this study is voluntary and any decision not to participate will not have any impact on how the subject's clinical treatment is performed. Patients will have a minimum of 24h to decide whether to participate or until the following visit by the District Nurses team (compression bandages are changed 2-3 times per week).

Following recruitment, a participant will be considered enrolled once he/she signs and dates the informed consent form. Once enrolled, the participant will be assigned a unique subject number, which will not contain information that could identify him/her (such as name or date of birth). The unique participant number will be used to label study data throughout the study.

All District Nurses in the organisation will be sent the Patient Information Sheet by their managers so that they will be well informed about the study aim and objectives. The research nurse might observe the application of compression bandaging. Patients receive care by a group of District Nurses, it is not unusual for patients to see 10-12 different District Nurses during the course of their treatment. Nurse participation is voluntary.

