# **APPENDIX 1: BASELINE MEASURES**

To determine the demographics and characteristics of the patients, the following baseline data will be collated:

Patient details

- Age
- Sex
- BMI [BMI will be calculated using weighing scales if available or by using the Mid Upper Arm Circumference (MUAC) technique when weighing scale are not available].
- Mobility status: does not walk / walks with assistance (stick/frame) / walks without assistance.

Medical history and status:

- Significant comorbidities, including CEAP Clinical score, Peripheral Arterial Disease,
   Diabetes (type I, type II, +/- neuropathy), Heart failure, Eczema, Rheumatoid
   Arthritis, Psoriasis, Other dermatitis, , Multiple Sclerosis, Cancer
- Any previous leg ulcers within last 2 years.

Index leg and ulcer status

- Leg ulcer aetiology determining need for compression bandaging: Venous, Mixed, Skin tear, Management of oedema, Lymphoedema, other traumatic wounds.

Compression care characteristics

- Location of regular leg care: home (self-care) / home (district nurse)/Ambulatory care
- Frequency of care (change of compression bandaging: .... per week.
- Specific dressing used on wound.
  - o no
  - Yes, which?
- Skin care product used on index leg before application of compression bandaging.
  - o No
  - Yes, namely: Hydromol

Nursing teams and setting

Where and by whom is the patient been seen?
 (Which DN team; Ambulatory clinics)

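### Nurse ease-of-use ratings are asked against an earlier bandage system that no form defines or records, and nurses' prior use of each brand is not collected

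*Protocol*

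**What the plan says.** In Appendix 3, the nurse questionnaire on application has a right-leg and a left-leg section with the same stem. The nurse scores five items from 1 (worst) to 6 (best) as overall "clinical experience of using this compression system compared to previously used compression system (please circle". The items themselves are plain questions such as "How easy is it to apply". The only product recorded in each section is the study bandage now on that leg: "S1F/S1R, S2F/S2R or S3F/ S3R (circle what applies".

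Table 1 (Timeline) schedules this form at Weeks 1, 4 and 8, and not at Week 0. The compression fields in Appendix 1 are location of care, "Frequency of care (change of compression bandaging: .... per week", wound dressing and skin product. The nursing field covers only team and setting: "Which DN team; Ambulatory clinics". The General questions at the end of Appendix 3 ask whether the nurse has a favourite bandage, which brand, and why.

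The Project summary says that bandage choice often follows nurse preference, "based on their acquired knowledge and skills of product application". The Research question section says it is unclear which system works best in the right patient, "at the right time and in the hand of the right clinician".

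**The concern.** A comparative question needs a known comparator. This stem is comparative, but its items and scale ends are absolute, and there is no midpoint meaning no change. One nurse may score the bandage on its merits. Another may score it against a former product. The completed form will not show which was done, or what the former product was.

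The second gap is in the study question. If acquired skill drives choice, and the aim includes the right clinician, then a nurse's earlier use of each brand is a context the study needs. Under the Theoretical framework, context is one of the three parts of every explanation. No form shown asks about it.

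At stake are the study's scored ease-of-use data, which would feed the selection guidance that the Data analysis section expects to produce.

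**Working it through.** The protocol gives no figure on this point to reproduce. The check is a reading of the forms, followed by a simple model of what does and does not cancel.

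**1. Possible readings of the stem.** The protocol does not choose among these.

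| Reading of the earlier system | Patient about to start compression | Over Weeks 1, 4, 8 | Shared by both legs? |
|---|---|---|---|
| Patient's product before the study | Does not exist | Fixed | Usually (Safety: normally one product for both legs), not always |
| Last bandage on that leg | Does not exist at first application | Becomes the study bandage after the first changes | No, once the legs differ |
| Nurse's own usual system | Exists | Fixed for a nurse, may differ with the rater | Yes, if one nurse rates both legs |

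The rater may well differ between visits. Recruiting and Screening says "it is not unusual for patients to see 10-12 different District Nurses during the course of their treatment". That figure is for a whole course of treatment, not for the 8 study weeks.

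**2. Is the reference recorded?** Neither Appendix 1, the patient and nurse clinical-experience form, the nurse application form nor the General questions has a field for an earlier compression product. None asks about a nurse's training in, or use of, each brand.

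**3. Ceiling on the data affected.** 40 patients × 3 visits = 120 forms. 120 × 2 legs = 240 leg ratings. 240 × 5 items = 1,200 item scores. This assumes one form per visit and full completion. Nurse participation is voluntary, so the real number will be lower. It counts scores, not error.

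**4. What cancels.** Write a leg's score as: constant + product effect + familiarity effect − reference + noise. The paste-minus-dry difference within a patient is then:

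(product difference) + (familiarity difference) − (reference on paste leg − reference on dry leg) + noise.

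- If both legs share one reference, the third term is zero.
- Absolute scores and comparisons across nurses or visits keep the reference.
- UrgoK2 and Coban2 are compared between patients, because each patient has only one dry leg under the Compression bandage selection procedure. The reference therefore stays in a direct comparison of their scores.
- The familiarity difference is specific to the product and does not cancel in any of these.

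**5. Illustration.** All inputs are assumptions; the protocol supplies none except n = 40. There is no true product difference, the noise SD is 0.8 and the reference SD is 1.0.

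- *Equal familiarity (50% of raters for each product), gain 0.5 to 1.5 points.* The mean paste-dry difference was about 0 in simulation. Its SE was 0.19 to 0.25 with a shared reference and 0.29 to 0.33 with separate, unrelated references. By formula at a gain of 0.5: shared √[(2 × 0.64 + 0.25 × 0.5)/40] = √(1.405/40) = 0.19; separate √[(1.405 + 2 × 1.0)/40] = 0.29.
- *Unequal familiarity.* The expected spurious difference is gain × (share familiar with paste − share familiar with dry).

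| Share familiar, paste / dry | Gain 0.5 | Gain 1.0 | Gain 1.5 |
|---|---|---|---|
| 30% / 80% | −0.25 | −0.50 | −0.75 |
| 20% / 90% | −0.35 | −0.70 | −1.05 |

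The simulation agreed to within 0.01. In this model an undefined reference adds noise to the paired contrast but does not bias it. Unequal familiarity biases it.

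**The case against.** Four stronger inferences are tempting, and the documents do not support them.

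- **That the reference changes over visits and ends as the study bandage itself.** This holds only if the earlier system means the last bandage on that leg. The form is about professional opinion and asks for the nurse's overall experience, so the nurse's own usual system is an equally natural reading. On that reading the reference stays fixed for a given nurse, and patients new to compression have one too. The supportable fault is ambiguity.
- **That product and habit cannot be separated.** The General questions ask for a favourite brand and the reason, and the per-leg form asks whether the nurse likes using the bandage. These allow a crude split. They are still preferences, which are what the study wants to explain, and a favourite says nothing about experience with the other two brands.
- **That the paste-dry comparison is spoiled.** One leg has paste and the other dry, and before the study both legs usually had the same product. If one nurse rates both legs, a shared reference largely drops out.
- **That a well-known brand will look easier.** All products are described as standard care, and the protocol reports no gap in familiarity. The differences in the illustration are conditional on assumed gaps.

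It is also fair to say that no comparison of mean ease scores is specified. The Data analysis section plans descriptive statistics where appropriate and inductive themes. In a realist evaluation, nurse habit is something to explain rather than adjust away. That limits the harm, but it strengthens the case for recording habit. It does not answer the mismatch between stem and items, which is fixed in the data form and which no later analysis can repair.

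**Conclusion.** The point holds as a fault in a fixed instrument. The nurse form asks for a comparison with a system that is not defined and that no form shown records, over items and scale ends that are absolute. Ratings may therefore rest on mixed references that the study data cannot recover.

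Up to 240 leg ratings carry the ambiguity. It bears on absolute scores, on comparisons across nurses and visits, and on direct comparison of UrgoK2 with Coban2. It bears much less on the paste-dry difference, provided that one nurse rates both legs and they share a reference.

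Separately, prior use of each brand is not collected, although the protocol makes acquired skill and the right clinician part of its question. Any bias from this depends on a familiarity gap that the protocol does not give. Under the assumed inputs it ranged from 0 (equal familiarity) to about 1 point on the 1 to 6 scale.

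The analysis is descriptive and theory-building, so the consequence is weaker interpretation and weaker support for the planned guidance. No statistical test is invalidated.

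**What to change.** 1. In both leg sections of the nurse application questionnaire, delete the clause that compares with an earlier system, and keep the absolute 1 to 6 scale.
2. Add to Appendix 1 the compression product on each leg immediately before the study, with none as an option.
3. Add a nurse study number to the nurse form, and one item, answered once per nurse, on prior use of or training in each of S1, S2 and S3.
4. Describe the ease scores by that item, alongside the existing favourite-brand answers.

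The cost is one deleted phrase, one baseline field per leg, a nurse number on the form and a short once-only nurse item. If any forms have already been completed on the present wording, mark them so that the two versions can be described separately.

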# b) Nurse recruitment

The nurses who are applying the compression bandages to the recruited patients will be asked questions about the ease of application. It is not possible to estimate how many nurses will be recruited, as a number of nurses will be looking after the above 40 patients, as per standard care.

- Nursing questionnaire for comfort at application, during wear and on removal, fluid handling (see Appendix 3)
- Nursing questionnaire asking ease of use/application (see Appendix 3).

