# Compression bandage selection procedure

The choice to apply 'full compression' versus 'reduced compression' will be dictated by the aetiology of the ulcer, wound assessment etc as per standard care. However, one leg will be bandaged in 'paste' compression and one leg in 'dry' compression, through a process of randomisation, using pre-prepared sealed envelopes.

The two types of compression bandages that will be used in this study are 'standard care' and are:

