# Data analysis

# **Refining Programme Theories**

Excel/word documents will be used to store data. The data collected from the recruited participants will be analysed collectively, using descriptive statistics where appropriate and inductively bringing together the various data sources in emerging themes. This will demonstrate how theories evolve in the course of the study. Engagement, involvement, and collaboration between each member of the research team will take place to refine theories to understand when, for whom and in what circumstances are two different types of compression bandages selected in clinical practice. It is hoped and expected that at the end of the study, new guidance for nursing staff will be developed to guide the selection of compression bandages.

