# **APPENDIX 3. PATIENT AND NURSE'S EXPERIENCE** PATIENT AND NURSE QUESTIONNAIRE – CLINICAL EXPERIENCE

Bandage used: Right Leg S1F/S1R, S2F/S2R or S3F/ S3R (circle what applies)	S1F = UrgoK2 S1R = UrgoK2 Lite S2F = Coban2 S2R = Coban2 Lite S3F = AndoFlex TLC Calamine S3R = AndoFlex TLC Lite Zinc
FOR THE PATIENT TO COMPLETE	
Please rate the following as your overall experience of circle):	of wearing this bandage (please
Has this bandage helped with your pain?	Yes No N/a
Has this bandage improved your comfort?	Yes No N/a
Has this bandage improved your ability to wear normal footwear and clothes?	Yes No N/a
Has this bandage stayed in place?	Yes No N/a
Has this bandage improved your skin condition?	Yes No N/a
Has this bandage improved your skin irritation?	Yes No N/a
Please add any further comment of your personal experience	
FOR THE NURSE TO COMPLETE	
Prior to last bandage application, was the leg washed with Hydromol mixed in warm water?	Yes No N/a
Prior to last bandage application, was the leg debrided using a debridement cloth or tenatome?	Yes No N/a
Looking at the leg, has this bandage helped improve the leg's skin condition?	Yes No N/a
Looking at the leg, has this bandage reduced the leg's skin irritation?	Yes No N/a
Looking at the leg, has this bandage helped with wound healing?	Yes No N/a

Looking at the leg, has this bandage helped with wound

malodour?

Yes

No N/a

	S1F = UrgoK2
	S1R = UrgoK2 Lite
Bandage used: Left Leg	
	S2F = Coban2
S1F/S1R, S2F/S2R or S3F/ S3R (circle what applies)	S2R = Coban2 Lite
	S3F = AndoFlex TLC Calamine
	S3R = AndoFlex TLC Lite Zinc

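### The nurse item on ease of removal is defined by signs of wear, so its single 1-6 score cannot be read as either removal effort or durability

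*Protocol*

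**What the plan says.** The item is in Appendix 3 of the protocol, in the nurse questionnaire on application, and is worded identically for the right and left leg: "How easy is it to remove? (i.e. Wear time – appearance of the bandage post wear – slippage, unwind, worn out areas".

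The instruction above it reads "On a scale of 1-6 (1 = worst, 6 = best) please rate the following as your overall", continuing "clinical experience of using this compression system compared to previously used compression system (please circle". The nurse therefore circles one number per item per leg, and the stated reference is the system used before, not the bandage on the other leg.

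The item just above has the same layout: "How easy is it to apply? (i.e. speed, technique required such as simple spirals and visual indicators for correct tension, cutting, tapes".

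Three other places bear on the point:

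- The section on nurse recruitment treats wear and removal as separate aspects: "Nursing questionnaire for comfort at application, during wear and on removal, fluid handling (see Appendix 3".
- The patient part of the clinical experience questionnaire asks, for each leg, "Has this bandage stayed in place", answered Yes, No or N/a.
- The section on bandage selection sets up a comparison within each patient: "one leg will be bandaged in 'paste' compression and one leg in 'dry' compression, through a process of randomisation, using pre-prepared sealed envelopes".

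The data analysis section plans to work by "using descriptive statistics where appropriate and inductively bringing together the various data sources in emerging themes".

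**The concern.** The bracket opens with *i.e.*, so it tells the nurse what the question means. Its contents (length of wear, look of the bandage afterwards, slipping, unwinding, worn patches) all describe how the bandage held up. None describes the time or effort needed to take it off.

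A nurse can answer the question or the bracket, and the answers may differ in direction. A bandage that has slipped or come loose may be easy to remove, which is a high score on the question, but has lasted badly, which is a low score on the bracket. A bandage that stayed firmly in place may be the reverse. One circled number does not show which was meant.

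What is at stake is the meaning of this one score. The protocol hopes to produce guidance on bandage selection, and ease of removal and durability could each matter to that choice. The fault lies in data capture: once a single number has been circled, no later analysis can separate the two components.

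**Working it through.** The protocol states no figure on this point, so there is nothing to reproduce. The check is a comparison of texts, a count and one illustration with assumed scores.

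**1. Does the bracket match the question?** In the application item, the bracket names speed, technique, cutting and tapes, all of which belong to applying a bandage. In the removal item, every entry belongs to the period of wear. The mismatch is specific to this item, and it appears on both leg forms.

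**2. Is either property captured elsewhere in Appendix 3?**

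| Property | Nurse forms | Patient form |
|---|---|---|
| Ease of removal | this item only | none |
| Durability or retention | this item's bracket only | the stayed-in-place question, Yes/No/N/a, per leg |

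The other graded nurse items cover applying, neatness once applied, learning and teaching. The nurse's part of the clinical experience form covers washing, debridement, skin condition, irritation, healing and malodour. Removal has no second source; retention has a partial one.

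**3. How many ratings are involved?** The inputs are 40 patients (sample section), 2 legs each, and Weeks 1, 4 and 8 for the nurse technical questionnaire (Table 1).

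40 × 2 × 3 = 240 leg-forms at most.

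The item is 1 of 5 graded items on each. The true number will probably be lower: nurse participation is voluntary, only Registered Nurses are eligible, and patients may leave early.

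**4. Can the reading alone change the ranking?** Let R be the removal rating and W the wear rating, and let w be the weight the nurse gives to the question rather than the bracket. Then

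score = w·R + (1 − w)·W.

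Assumed values, not taken from the documents: paste R = 3, W = 5; dry R = 5, W = 3; the same w for both legs. The paste-minus-dry difference is

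w(3 − 5) + (1 − w)(5 − 3) = 2 − 4w.

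| w | Paste | Dry | Paste − dry |
|---|---|---|---|
| 1 (question only) | 3 | 5 | −2 |
| 0.75 | 3.5 | 4.5 | −1 |
| 0.5 | 4 | 4 | 0 |
| 0.25 | 4.5 | 3.5 | +1 |
| 0 (bracket only) | 5 | 3 | +2 |

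With these scores, the same two bandages rank either way depending only on how the item is read.

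**5. Where does this stop?** In general the difference is w·(difference in R) + (1 − w)·(difference in W). If one type is better on both properties, both terms have the same sign, and for a common w the score favours that type whatever w is. The reader still could not tell which property was responsible. A reversal needs the two properties to disagree, and the documents contain no data on how often they do.

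**6. Is w likely to be stable?** The recruitment section says it is not unusual for a patient to see 10-12 different District Nurses. Even if each nurse reads the item the same way for both legs, the reading can change between visits for the same patient.

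**The case against.** The strongest case on the other side is that this is a minor wording fault with little consequence.

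- *The analysis is descriptive.* The protocol names no primary endpoint, test or total score for this questionnaire, and the item sits beside pain and pruritus scales, EQ-5D-5L, VEINES-QoL, photographs and other questions. This stands. No error rate, power or sample size is affected.
- *Other information exists.* Patients report per leg whether the bandage stayed in place and may comment. Nurses say whether they like the bandage, and give a preferred brand with reasons. This stands in part: retention is partly covered. The nurse answers concern overall liking and would not reliably show how the removal item was read, and ease of removal has no other item.
- *Opposite directions are plausible but not shown.* This stands. The protocol describes the paste system and one of the dry systems (Coban2) as having the same build, a foam layer under a cohesive short-stretch layer, so its product descriptions give no clear reason to expect paste and dry to differ in how firmly they cling.
- *Even a perfect item would not compare paste with dry directly,* because ratings are made against the previously used system. This stands, and the fix does not remove it.

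A reader might go further and infer that the trial cannot rank paste against dry on removal or durability at all, or that the item will mislead by as much as 5 points. The documents support neither. The first overlooks the patient's retention question and the case in which one type is better on both properties. The second is simply the width of a 1-6 scale (6 − 1 = 5), not an estimate of error.

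**Conclusion.** The point holds, within limits. On both leg forms the removal item asks one thing and defines another, so its score cannot be read as ease of removal or as durability. Ease of removal is measured nowhere else; retention is partly measured by the patient's answer.

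The effect is on the interpretation of one descriptive nurse item, 1 of 5 graded items on up to 240 leg-forms. It does not overturn any planned conclusion. How far the score would mislead in practice is unknown: that depends on how often the two properties disagree and on how nurses read the item, and the documents are silent on both. The −2 to +2 range in the illustration follows from assumed scores and shows only that a reversal is possible.

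The change is worth making because it is cheap and because the ambiguity cannot be resolved after the data are collected.

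**What to change.** On both leg forms, replace the item with two:

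1. Keep the existing question on ease of removal, with a bracket that fits it: *(e.g. time, effort, cutting, sticking to skin or dressing)*.
2. Add: *How well had it lasted since the last application? (slippage, coming unwound during wear, worn-out areas)*.

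Rate each 1-6 under the existing instruction (1 = worst, 6 = best), with the same reference to the previously used system as the other items. Do not give the second item an absolute anchor of its own, since that would clash with the comparative instruction. Unwinding should appear only as a failure during wear, so that the overlap does not return.

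Report the two scores separately, and set the second beside the patient's answer on whether the bandage stayed in place. State in the report that paste and dry are compared only indirectly, through ratings against the earlier system.

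Cost: one extra line per leg and a form version change. Forms already completed cannot be split, so their removal scores should be reported apart from those on the new version.
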